8.4 Criteria for Premature Study Discontinuation

The Protocol Chairs and SRV Site PIs have the authority to withdraw any participant at any time if in their opinion it would be in the best interest of the participant. The participant will be informed of this withdrawal and explained the rationale. Withdrawal will be documented in the study tracking system. If a participant is withdrawn due to seroconversion, they will be offered referrals and linkages as necessary, and may be referred to an ATN study for HIV+ participants.

Participants will be prematurely discontinued from the study if any of the following occurs:

- The participant withdraws consent/assent
- The participant is unwilling or unable to comply with study procedures
- The participant fails to return or confirm HIV negative test results with research staff within 90 days of their enrollment visit
- The participant returns a HIV positive test result at the 3- or 6-month follow-up time point.
- The participant seroconverts
- The Protocol Chairs or Site PIs believe that ongoing participation may cause harm to the participant or study staff
- The Protocol Chairs or Site PI believe that ongoing participant may impact the integrity of the study dataThe study is cancelled by the NIH (or iTech, or other administrative entity);
- The study is cancelled for other administrative reasons;
- Death of the participant

Participants may end their participation in the study at any time. No further data collection will occur from the date the decision is made to permanently discontinue the subject from the study. Participants who experience distress during the study while in the SRV clinic will be offered counseling on site. Participants who experience distress during the study and do not come to the SRV clinic for a visit will be provided a list of community referrals via phone or e-mail. Any unexpected adverse events that meet the unanticipated problem (UP) reporting criteria will be immediately reported to the UNC-CH IRB and the respective sites' IRBs if applicable. The *Study Stop CRF* will be completed at this time.

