Although systematic review indicates that mobile health interventions are particularly efficacious at increasing HIV protective behaviors among vulnerable and key HIV risk populations such as trans youth,²⁸ a recent systematic review revealed that only 18% of mobile phone-based HIV prevention/care interventions provide any information tailored to LGBT populations, and none were tailored specifically to trans individuals.²⁹ One digital intervention designed for LGBT youth, but not specifically tailored for trans youth, successfully increased safer sex outcomes among participants,³⁰ and another intervention designed for young African American/Black MSM and trans women, but was not specifically for trans women, demonstrated significant improvements in participant social support, social isolation, and depressive symptoms.^{31,32} The TechStep study will fill a critical gap in the scientific advancement of technology-based interventions for trans youth by a) creating the first technology-based trans youth-specific HIV prevention interventions optimized for mobile phone delivery; and, b) employing the two intervention delivery modalities identified as most promising for use among trans YYA (i.e., text messaging and mobile app).

As part of the UNC/Emory Center for Innovative Technology (iTech), we propose to test the efficacy of TechStep for trans YYA. In this 4-year study, 275 high-risk trans YYA between the ages of 15-24 will be randomized to receive text messaging, a WebApp, or an information-only control intervention for 6 months, with assessments occurring at baseline and 3-, 6- and 9-months. YYA who do not evidence improvements in sexual risk and/or PrEP uptake at the 3-month assessment will be randomized to either receive weekly eCoaching sessions in addition to their assigned text messaging or WebApp intervention, or remain in the original intervention in a 2:1 ratio. The primary endpoint is reduced sexual risk behaviors and/or PrEP uptake, adherence and persistence at month 6.

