6.4. Premature Discontinuation/Off-Study Evaluations/Measures

Participants who discontinue study participation during the focus group will be asked to provide a reason for discontinuing the study and paid the full compensation amount. Participants who discontinue study participation during the RCT will be asked to provide a reason for discontinuing the study and provided compensation consistent with their participation up to that point.

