8.0 PARTICIPANT MANAGEMENT

8.1 Tracking Participants / Follow-up

Study staff will verify participant contact information at baseline and update this information if needed at time of follow up.

Study staff will contact participants prior to their target date to complete follow-up study procedures. Study staff will use both a preferred and, if necessary for YYA who are difficult to reach, backup method of contact as indicated at baseline (e.g. mail, alternate phone numbers, e-mail, text message, social media contact information), to contact participants to complete follow up study procedures. Additional reminders will be provided on/after the target date as needed to ensure completion of study visit procedures. Participants will be asked whether or not messages can be left for each of the phone numbers that they provide. They will be informed that messages will not contain any information regarding the nature of the project.

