2. Protecting against hostile interactions and inaccurate information from one participant to another. Participants will be informed during the onboarding process of the "group rules" regarding interactions with one another (e.g., "Honesty is important; however, hostile or abusive language will not be tolerated and may be grounds for immediate removal from the study"). These "rules" will also be available with a link on all intervention web pages for review by participants at any time. The project coordinator will manually review an automated compilation of posts participants make on a daily basis to flag hostile interactions and inaccurate information. Hostile interactions between participants will be handled by, first, reminding the participants in the interaction of the "group rules" regarding appropriate interactions. If the hostility continues, the offending participants will be given a warning that the continued hostility will result in withdrawal from the study if it continues. On the third offense, the participant may be withdrawn from the study after discussion of the offense. Text containing hostile exchanges will be removed from the study website and unavailable to view. In cases in which inaccurate information is found, project staff be guided by experts on the team to post a comment that provides accurate information on the topic. In extreme cases, the Protocol Chairs or SRV Site PIs may decide to withdraw a participant before the third offense. We will ensure all clinic sites have a clear clinical protocol to address major issues that may come up at study visits or in online interactions. The major issues addressed in the protocol will be suicidal ideation, homicidality or violent ideation, emotional and cognitive disregulation, violent/aggressive or disruptive behavior, and intoxication. If research staff see concerning comments or messages online from participants regarding self-harm or harm of others, they will contact study site staff and take immediate precautions.

All sites have specific policies governing the treatment of human subjects. These policies specify that medical and psychological assistance will be available in the immediate environment in the event a participant should experience any adverse reactions resulting from study procedures.

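### Section 8.4 ends all data collection for undefined non-compliance and for a discretionary data-integrity judgement, which permits arm-dependent loss of outcomes that LTMLE may only partly correct

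*Combined protocol and SAP*

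**What the plan says.** Section 8.4 lists events after which a participant will be discontinued. Two matter here. One is "The participant is unwilling or unable to comply with study procedures". The other is a belief of the Protocol Chairs or site PI that "ongoing participant may impact the integrity of the study" data. The consequence is stated without exception: "No further data collection will occur from the date the decision is made to permanently discontinue the subject from the study". Section 6.4 adds little for people who leave: "Participants who discontinue study participation during the RCT will be asked to provide a reason for discontinuing the study", and they are compensated for participation to that point. No outcome items are offered to them.

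The demands on participants differ by arm. Info participants have access to information and attend assessments. Participants who step up are to receive "weekly eCoaching sessions in addition to their assigned text messaging or WebApp intervention" (Section 1.1). Section 8.3, under the risks of receiving the WebApp, sets a conduct rule for its users: "On the third offense, the participant may be withdrawn from the study after discussion of the offense". In extreme cases, "the Protocol Chairs or SRV Site PIs may decide to withdraw a participant before the third offense".

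Section 10.3.2 plans LTMLE with a dropout regression that adjusts for baseline and time-varying covariates, and Section 10.4 relies on it for missing data. The Study Abstract says that activity data will be collected at each intervention step and in the control condition. Section 10.3.2 does not name these data as covariates.

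**The concern.** A rule that turns non-compliance into complete loss of follow-up lets post-randomization behaviour decide whose outcomes are observed. If what counts as compliance differs by arm, so can the loss. Suppose a site treats missed coaching as non-compliance. Of two similar month-3 non-responders, the one assigned to eCoaching could be discontinued, while the one left on text or app has no sessions to miss. Aim 3 would then compare eCoaching attenders with a comparator that kept everyone. The Text+Step and App+Step contrasts with Info would inherit part of the distortion.

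The integrity criterion raises a related issue. It is a judgement made after randomization, with no objective test, by leads who are not described as masked and who also rule on WebApp conduct. A covariate model cannot represent an opinion that no variable records.

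**Working it through.** **1. Does the rule reach intervention use?** The text supports two readings.
- Narrow: Section 8.1 says "Study staff will contact participants prior to their target date to complete follow-up study procedures". There the term refers to assessments, which all arms share.
- Broad: Section 5.0 is titled Study Procedures. It contains Section 5.3 on intervention procedures, and Section 5.3.3 covers stepping to eCoaching and scheduling its sessions.

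Section 8.4 uses the unqualified term, so sites could apply it differently.

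**2. The plan's own figure.** Section 10.2.2 gives more than 80% power for a decrease of 1.5 encounters with 5-15% dropout, from simulation. SD, alpha, arm means and covariate strength are not given, so the figure cannot be reproduced. For scale only, assume two-sided alpha 0.05, 83 per arm and 15% dropout (70.55 per arm). The largest SD that gives 80% power is 1.5 / [(1.960 + 0.842) × √(2/70.55)] = 3.18. With no dropout it is 3.45.

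**3. Formula.** Let d be the share removed in a group. Let D be the mean difference in risky encounters (removed minus retained) that remains after adjustment, taken as equal in both groups. The retained mean is the full mean minus d × D, so the bias in the contrast is −(d_active − d_control) × D. A negative value flatters the active arm; if removed participants had fewer encounters, the sign would reverse.

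**4. Results.** The values 5% and 15% are the ends of the dropout range in Section 10.2.2. The split between groups and all values of D are assumptions. Cells show the size of the bias in encounters and as a share of 1.5.

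| Removed, active vs control | D = 1 | D = 1.5 | D = 3 | D = 5 |
|---|---|---|---|---|
| Equal | 0 | 0 | 0 | 0 |
| 10% vs 5% | 0.05 (3%) | 0.075 (5%) | 0.15 (10%) | 0.25 (17%) |
| 15% vs 5% | 0.10 (7%) | 0.15 (10%) | 0.30 (20%) | 0.50 (33%) |

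**5. Type I error.** For an unadjusted test on retained participants at 15% vs 5% removal with SD 3.18, the SE is 3.18 × √(1/70.55 + 1/78.85) = 0.521. A nominal 5% error becomes 5.4%, 6.0%, 8.9% or 16.0% for D = 1, 1.5, 3 or 5.

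**6. Aim 3.** The active arms hold 108 + 83 = 191 participants. If 30%, 50% or 70% are re-randomized (assumed), about 57, 96 or 134 enter. Read as 2:1 in favour of eCoaching, as in Section 5.3.3, they split about 38/19, 64/32 or 89/45. At the smallest size, 4 removals are 4/38 = 11% of the eCoaching group. Section 3.1 lists the two options in the opposite order, and the two sections must be reconciled.

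**7. Dilution in the primary contrast.** If the excess removal occurs only in the eCoaching group, and half of an active arm is re-randomized with two-thirds getting eCoaching, that group is 0.5 × 2/3 = 1/3 of the arm. The 0.10 to 0.50 of step 4 then becomes 0.03 to 0.17 encounters (2% to 11% of 1.5).

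**The case against.** The strongest reply is that the clause concerns assessments only. No section makes use of texts, app or eCoaching a condition of staying in the study. Retention effort points the other way: Section 8.1 provides backup contact methods and extra reminders, and Section 5.3.3 allows visits 75 to 90 days late. Engagement is measured, and LTMLE is chosen partly because it handles informative missingness.

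Much of this stands. A reader might infer that Section 8.4 removes non-engagers, and mainly from the more demanding arms. The documents do not support that: the broad reading is available but not stated, and no removal rate by arm is given. Extra coaching burden makes differential removal plausible, not established. It would also be wrong to call engagement unmeasured, since process data are collected.

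The reply does not settle the matter. The wording in Section 8.1 is qualified, while the headings of Section 5 cover the interventions. The WebApp conduct rule is written for one arm and leads out of the study, not just off the message wall. Section 10.3.2 claims reduced bias, which holds as far as measured covariates explain removal. If a site discontinued nearly all non-attenders, no similar participants would remain under observation to stand in for them, and adding attendance to the model could not recover their outcomes. No missing-data sensitivity analysis is described.

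**Conclusion.** The point holds as a risk created by the wording. Section 8.4 mandates loss of all further data on an undefined criterion and on a discretionary one, and the protocol permits that loss to depend on arm. Bias in Aim 3 or in the active-versus-Info contrasts is possible but not demonstrated.

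The illustrative size is 0.05 to 0.50 encounters, or 3% to 33% of the 1.5 target, over the unequal splits tried, and zero if removal and gaps are equal. These values rest on an assumed split and an assumed residual gap. The 1.5 benchmark belongs to the primary analysis and is only a yardstick for Aim 3.

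A reader might reach larger figures by assuming that 10% to 20% of the eCoaching group is removed, none of the comparator, and a gap of 5: 0.5 to 1.0 encounters, or 33% to 67% of 1.5. The documents do not support those inputs. The upper rate exceeds the whole dropout range in Section 10.2.2, zero comparator removal is the extreme case, and a gap of 5 is about 1.6 times the SD of 3.18 (5/3.18).

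The change is worth making because it is cheap and protects both randomizations.

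**What to change.** - **Section 8.4:** define compliance with study procedures. State that non-use of texts, app or eCoaching, or removal from the WebApp message wall, ends only that component. The participant stays in the assigned arm and is invited to every remaining ACASI unless consent or assent is withdrawn. Align Section 8.3 with this.
- **Integrity removals:** have the Analytic Core decide them without knowledge of arm. Report all removals by arm and reason from the existing Study Stop CRF.
- **Section 6.4:** offer the sexual-risk and PrEP ACASI items to leavers who agree.
- **Section 10.3.2:** name the process data as time-varying covariates in the dropout model.
- **Unchanged:** the HIV-test, seroconversion and safety criteria stay as they are.

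The cost is amendment wording. The ACASI is already scheduled and online, so no new visits are needed. The downside is more follow-up contacts for disengaged participants and an eCoaching estimate that may be smaller. Ordinary non-response will remain, so the change removes this source of bias and not all missing-data bias.

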9.0 MONITORING UNTOWARD EFFECTS ASSOCIATED WITH OR RESULTING FROM STUDY

9.1 Site research staff must first follow their own IRB's procedure for reporting and managing untoward effects.

There are three types of untoward effects to be identified: (1) those related to the participant, (2) those related to the study staff, and (3) those related to the neighborhood/community (*if applicable*).

First, the study will catalogue any untoward effect related to the participant. Reporting is required for occurrences including social harms, psychological distress, and serious life-threatening events such as suicide attempts. These may be immediately apparent to the study staff, such as the participant's emotional upset state requiring referral for counseling; or they may be delayed and reported later to study staff, such as physical harm to an individual for having participated in the study. Study staff will notify the iTech team of these untoward effects using the iTech QNS accessible through the iTech website (www.iTechnetwork.org) within 24 hours of becoming aware of these untoward effects. Study staff will be briefed during the training on the scope of possible untoward effects and instructed to report events.

Second, study staff may encounter untoward events during the focus groups or RCT that personally affect them. Training and guidance will seek to minimize this risk. Nonetheless, an assessment of the cost of conducting this study must include cataloguing these events as well. The protocol chairs should be notified of these events so that they may be immediately addressed, evaluated, and guidance modified or expanded to minimize similar risk to other study staff.

Third, a critically important area any community-based study intends to evaluate is the impact, including untoward effects, of the project on the community. This will be done informally for this protocol with untoward events being reported to the protocol team.

All untoward effects/adverse events/unanticipated problems will also need to be reported to the UNC IRB if they meet all three of the following criteria:

“Unanticipated problems involving risks to subjects or others” (UPIRSO) refers to any incident, experience, or outcome that:

- 1) is unexpected (in terms of nature, severity, or frequency) given (a) the research procedures that are described in the protocol-related documents, such as the IRB-approved research protocol and informed consent document; and (b) the characteristics of the subject population being studied;
- 2) is related or possibly related to a subject's participation in the research; and
- 3) suggests that the research places subjects or others at a greater risk of harm (including physical, psychological, economic, or social harm) than was previously known or recognized.

Events that meet the criteria for an UPIRSO and are also serious adverse events should be reported to the UNC IRB within one (1) week of the investigator becoming aware of the event.

Any other events that meet the criteria for a UPIRSO should be reported to the IRB within two (2) weeks of the investigator becoming aware of the problem.

If the report cannot be completed in its entirety within the required time period, a preliminary report should be submitted. The report should be amended once the event is resolved and/or more information becomes available.

10.0 STATISTICAL/ANALYTIC CONSIDERATIONS

10.1 Introduction

10.1.1 Focus Groups Overview

We will conduct eight focus groups with up to 10 trans YYA (one group with youth 15-20 years old and one group with young adults 21-24 years old) at 4 SRVs (Houston, Los Angeles, New York, and Philadelphia). Focus groups in Houston and Los Angeles will be used to obtain information specific to the Web App. Topics covered in those focus groups include: 1) challenges to obtaining culturally appropriate and comprehensive sexual health and other health services; 2) feedback from trans YYA about the “look and feel” and content of the original TWM and YouTdrive interventions; 3) suggestions for adapting the intervention for trans YYA similar to themselves. Focus groups in New York and Philadelphia will be used to obtain information specific to the text messaging intervention. Topics covered in those focus groups include: 1) feedback from the trans YYA about the adaptation of the *Text Me, Girl!* text-message library for HIV-positive young trans women to high-risk trans feminine, trans masculine, and gender non-conforming HIV-negative YYA; 2) specific editing of text messages for content that is culturally appropriate and relevant to HIV-negative trans YYA; 3) suggestions on content and appropriateness of text messages related to trans-specific sexual health; 4) suggestions on content and appropriateness of text messages related to biobehavioral HIV prevention strategies (e.g., PEP/PrEP). Focus groups (as opposed to in-depth quantitative interviews) were chosen to gain feedback in these areas because this setting will allow participants to explore together the ways in which the TechStep intervention meets their needs and how the intervention can be adapted to be community appropriate.

10.2 Power Estimates

10.2.1 Focus Groups Power Considerations

The purpose of focus groups is not to obtain generalizable data, but rather to obtain collective qualitative information to inform adaptation of the existing interventions for trans YYA. We are balancing feasibility with the need to obtain information from a spectrum of trans youth. As such, we will conduct 8 focus groups, targeting youth (ages 15-20) and young adults (ages 21-24) at 4 different SRVs with the goal of reaching a maximum of 80 trans YYA. Given our prior experience and best practices for the conduct of focus groups, this will provide us with information from enough YYA to inform the adaptation process.

10.2.2 RCT Power Considerations

We performed extensive Monte Carlo simulations to assess the power for our primary analysis. We examined scenarios involving different dropout rates (5-15%), different relative efficacies of first-line (text or app) interventions relative to the eCoaching intervention, and different levels of strength of predictive covariates to be included in the analysis. Across a wide range of scenarios, we determined that we will have >80% power to detect a clinically meaningful effect, defined as an average decrease of at least 1.5 risky sexual encounters over the course of the study.

10.3 Statistical Analysis Plan

10.3.1 Analyses of Focus Group Data.

Focus group discussions will be transcribed verbatim from the digital audio-recording, de-identified by assigning unique numerical codes, and entered into Dedoose software to assist with theme identification, coding textual data, and describing relationships among codes (via code co-occurrence and memoing functions). Following established focus group analysis guidelines, we will create a codebook of a priori and emergent themes including operational definitions of all codes and sample quotations to illustrate how to apply each code. Two study team members will then use the codebook to independently code the compiled user profiles while a third team member will review these sections of coded data and resolve discrepancies. We will draw a random sample of 20 instances for the coders to begin with and calculate an inter-rater reliability score based on their code assignments. If this score is <95%, we will refine the codebook definitions and retrain the coders. Coders will then complete the coding of the remaining instances and we will calculate an inter-rater reliability score. Discrepancies will then be reviewed and resolved by the research team. Coding and analytic activities will be discussed during weekly team meetings.

